13.3.4 Surgical Plan Changes

The proportion of patients in whom the Pre-Fluorescence Surgical Plan was changed based on fluorescent imaging, both prior to initiation of the surgical procedure and upon reimaging of the surgical field after the surgical procedure immediately prior to surgical closure, will be estimated along with 95% CIs.

13.3.5 Pharmacokinetics

The pharmacokinetics (PK) of OTL38 will be estimated by fitting compartmental pharmacokinetic models to the serial plasma concentration-time (Ct) data using established methods including maximum likelihood parameter estimation and nonlinear mixed-effects (NLME) modeling approaches, with the patient serving as the random effect. Various structural PK and error models will be fit to data using a qualified, standard software package. Primary PK parameters will be estimated at the population level and for individual patients as post-hoc empirical Bayesian estimates (EBEs). The actual primary parameters may vary depending on the supported model, but are likely to include systemic clearance (CL), volumes of distribution of the central and peripheral compartment(s) (V_c , V_p), distributional clearance (CL_d), or derivatives thereof. Inter-patient variability in select PK parameters will be assessed as part of the model, as will the residual error. Secondary parameters may include, but are not limited to: model predicted maximum concentration (C_{max}), time of C_{max} (T_{max}), area under the concentration-time curve (AUC) to the last time point (AUC_{last}) and to infinity (AUC_{inf}), and the terminal elimination half-life ($T_{1/2}$). The model predicted Ct profiles and observed Ct data will be presented as figures for the population and individual level. Individual primary EBE and secondary parameters will be presented as listings at the patient level.

Potential covariates explaining inter-subject PK variability, and their influence upon PK parameters, will be initially screened using a two-stage approach with standard parametric statistical tests on the individual patient EBEs, focusing on CL. Covariates of interest will include baseline demographic values (e.g. height, weight, age, BSA, BMI, race), and laboratory values predictive of renal or hepatic function (e.g. BUN, creatinine, calculated creatinine clearance or GFR, AST, ALT, alkaline phosphatase, albumin, and total bilirubin). If warranted, a single stage approach with direct incorporation of covariates into the NLME PK model may be undertaken using a forward addition - backward deletion method at an alpha level of 0.05.

The final model PK parameter estimates, and any bootstrapped results, will be reported as a table, including the estimates, their standard errors, or confidence intervals. The covariate coefficient estimates, their standard errors, and the associated P values for those significant at the alpha level of 0.05 will be tabulated. Relationships between covariates and PK parameters will be graphically presented as figures. Additional details will be found in the pharmacokinetics analysis plan (PKAP).

13.3.6 [REDACTED]

Descriptive summary statistics for [REDACTED] pre-surgery (baseline), post-surgery, and the change from pre-surgery will be calculated along with the percent change. In addition, the number

and percent of patients whose post-surgery [REDACTED] have increased, decreased, or remained the same as pre-surgery [REDACTED] will also be provided. This analysis will use all patients with non-missing [REDACTED]

13.4 Handling of Missing Data and Subject Withdrawals

For the primary efficacy endpoint, all patients included in the FAS with at least one evaluable lesion will be included in the primary analysis.

For secondary and exploratory efficacy endpoints, patient inclusion for the analysis of a specific endpoint will depend on the lesion type or patient subgroup under specific consideration.

In general, missing safety data will not be imputed with the possible exception of missing or partial dates for adverse events and concomitant medication.

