8.3 Handling of Missing Data, Subject Withdrawals, and Treatment Failures

For the primary efficacy endpoint, all subjects included in the FAS will be included in the primary analysis.

For secondary and exploratory efficacy endpoints, patient inclusion for the analysis of a specific endpoint will depend on the lesion type or patient subgroup under specific consideration.

In general, missing safety data will not be imputed with the possible exception of missing or partial dates. Details will be included in the SAP.

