8.1 Full Analysis Set (FAS)

The FAS for the primary analysis of the primary endpoint will include patients exposed to OTL38 and randomized to undergo fluorescent imaging (OTL38+Imaging) who:

- Were evaluated under both normal light and fluorescent light imaging, and
- Had central pathology and histology confirmation for at least one FR+ Ovarian Cancer lesion detected under normal light or fluorescent light imaging

For the evaluation of the primary efficacy endpoint, only the evaluable lesions contributed by FAS subjects will be considered (see Section 8.4). The FAS will also be referred to as the modified Intent-to-Treat (mITT) analysis set.

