8.4 Evaluable Lesions

Evaluable lesions are defined as follows: lesions that do not appear on an organ or tissue that was intended for removal regardless of the absence or presence of tumor based on the Pre-Fluorescence Surgical Plan.

The primary efficacy endpoint will be determined based on evaluable lesions for FAS subjects.

Unless otherwise specified, exploratory efficacy endpoints [REDACTED]

[REDACTED] sensitivities, FPRs, and PPVs for FR+ with ovarian cancer and other disease+/test+ configurations will be estimated using lesions without regard to evaluable lesion status.

Efficacy endpoints calculated without input from lesion data will be estimated without regard to evaluable lesion status.

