12 EFFICACY EVALUATIONS

12.1 Primary Efficacy Endpoint

The primary efficacy endpoint is the proportion of patients with at least one evaluable FR+ ovarian cancer lesion confirmed by [REDACTED] pathology [REDACTED] that was detected using the combination of OTL38 and fluorescent light but not under normal light or palpation. [REDACTED]

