12.2 Secondary Efficacy Endpoints

- False Positive Rate at the patient level (FPRp) will be a major secondary efficacy endpoint and is defined as the proportion of folate positive ovarian cancer patients in whom all lesions, without regard to evaluable lesion status, detected by fluorescent light only are histologically negative.
- Sensitivity or True Positive Rate (TPR) for OTL38 in combination with fluorescent light: [REDACTED]
- False Positive Rate (FPR) for OTL38 in combination with fluorescent light: For the purpose of this protocol, [REDACTED]

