13 STATISTICAL ANALYSIS METHODS FOR EFFICACY

The primary analysis of the primary efficacy endpoint will be conducted using the evaluable lesions for FAS subjects. Analyses of secondary and exploratory efficacy endpoints will use the FAS with additional, or modified, criteria as appropriate and as described in Section 8.4 and below. Baseline values are defined as the last non-missing value for a particular efficacy endpoint recorded prior to exposure to study drug. Unless otherwise noted, all p-values will be two-tailed and all confidence intervals two-sided.

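### SAP 13.4 drops full-analysis-set patients without an evaluable lesion from the primary analysis, protocol 8.3 keeps them, and only non-successes can be dropped

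*SAP*

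**What the plan says.** The two documents define the primary denominator in parallel sections on missing data and withdrawals.

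- Protocol 8.3: "all subjects included in the FAS will be included in the primary analysis".
- SAP 13.4: "all patients included in the FAS with at least one evaluable lesion will be included in the primary analysis".

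The other SAP sections restrict which lesions count, not which patients count. SAP 8.1 says that "only the evaluable lesions contributed by FAS subjects will be considered", and SAP 13 says that "The primary analysis of the primary efficacy endpoint will be conducted using the evaluable lesions for FAS subjects".

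Three definitions decide what the added condition does.

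- FAS entry (SAP 8.1), for imaged patients: "Had central pathology and histology confirmation for at least one FR+ Ovarian Cancer lesion detected under normal light or fluorescent light imaging". The lesion need not be evaluable.
- Evaluable lesions (SAP 8.4): "lesions that do not appear on an organ or tissue that was intended for removal regardless of the absence or presence of tumor", judged from the surgical plan made before fluorescence.
- Primary endpoint (SAP 12.1): "the proportion of patients with at least one evaluable FR+ ovarian cancer lesion" that fluorescence found and normal light and palpation did not.

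No visible SAP text, including section 16 on changes to planned analyses, mentions or justifies a departure from protocol 8.3.

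**The concern.** A patient whose only lesions lie on organs already scheduled for removal is in the FAS but has no evaluable lesion. Protocol 8.3 counts her as a non-success; SAP 13.4 leaves her out. The same data can therefore give two primary results, and the SAP is unclear within itself about which one it intends.

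The condition also depends partly on the test being evaluated. Take a patient with no evaluable lesion under normal light. If fluorescence marks an evaluable lesion, true or false, she is counted. If it marks none, she disappears from the denominator. False-positive patients are expected, since SAP 12.2 makes a secondary endpoint of the proportion "in whom all lesions, without regard to evaluable lesion status, detected by fluorescent light only are histologically negative".

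This is the denominator of the single confirmatory test in an open-label pivotal trial. Left open, it could be settled after results are known, and one of the two choices can only favour the product. The only visible sensitivity analysis (SAP 13.1.2) uses the per-protocol set, which is a subset of the FAS and follows the primary methods, so it would not show the effect.

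**Working it through.** **Direction, from the definitions alone.** Let N be the FAS size, x the successes and k the FAS patients with no evaluable lesion. A success requires an evaluable lesion, so none of the k can be a success. Protocol 8.3 gives x/N and SAP 13.4 gives x/(N − k). The numerator is fixed, so the estimate is multiplied by 1/(1 − k/N): 1.05 at k/N = 5%, 1.11 at 10%, 1.25 at 20%.

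**The plan's own figure.** The protocol synopsis requires at least 100 evaluable patients. This cannot be reproduced, because the null proportion, the assumed proportion and the power are redacted. The visible text does not define an evaluable patient.

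**Inputs for the illustration**
- From the documents: one-sample exact binomial test, two-tailed alpha 0.05 (protocol 8.2.5.1, SAP 13.1), taken as 0.025 in the upper tail.
- Assumed: N = 100 FAS patients; null p0 = 10% (range 5% to 20%); E = share with no evaluable normal-light lesion; f = share of that group's non-successes kept in by an evaluable false-positive lesion; success independent of E.

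**Formulas.** A patient is left out with probability d = (1 − p) × E × (1 − f). The retained n is Binomial(100, 1 − d), and successes given n are Binomial(n, p/(1 − d)). The test rejects when successes reach the smallest c with P(Bin(n, p0) ≥ c) ≤ 0.025. For n = 100 and p0 = 10%, c = 17 with tail 2.06%. All results are exact, without simulation.

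*1. Upper-tail error if the null applies to the whole FAS (p = p0 = 10%).* Example: E = 20%, f = 0 gives d = 0.90 × 0.20 = 0.18, and the retained success probability is 0.10/0.82 = 12.2%.

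| E | 0 | 2% | 5% | 10% | 20% | 30% |
|---|---|---|---|---|---|---|
| f = 0 (upper bound) | 2.06% | 2.07% | 2.53% | 3.85% | 7.66% | 14.15% |

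At E = 20% the error is 5.34% for f = 25% and 3.85% for f = 50%. Over f = 0 to 50% at E = 20%, it is 5.48% to 2.88% for p0 = 5% (base 1.15%) and 11.55% to 5.10% for p0 = 20% (base 2.00%).

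*2. Chance that the SAP denominator rejects and the protocol denominator does not (p0 = 10%).* The reverse did not occur in any case computed.

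| True rate | f | E = 5% | E = 10% | E = 20% |
|---|---|---|---|---|
| 15% | 0 | 2.5% | 9.4% | 21.7% |
| 15% | 50% | 0.2% | 2.5% | 9.4% |
| 20% | 0 | 1.6% | 5.7% | 11.0% |
| 25% | 0 | 0.2% | 0.9% | 1.5% |
| 30% | 0 | <0.1% | <0.1% | <0.1% |

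*3. Reported proportion when the true FAS rate is 20%.* The formula is p/((1 − E) + E·p + E·(1 − p)·f). At E = 20%, f = 0: 0.20/(0.80 + 0.04) = 23.8%. For E = 5% and 10% it is 20.8% and 21.7%. With f = 50% the three values are 20.4%, 20.8% and 21.7%.

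*4. By number of patients left out (p-value = twice the upper tail, p0 = 10%).* 16/100 gives p = 0.080; 16/94 = 17.0% gives p = 0.048; 16/80 gives p = 0.011. For p0 = 5%, 20% and 30%, the nearest miss becomes significant after 2, 3 and 2 exclusions.

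**The case against.** The strongest reply has four parts.

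- **Loose drafting.** SAP 13.4 is a missing-data section that says who is included and never says the others are dropped. SAP 8.1, 8.4 and 13 restrict lesions only. This may be so, but the sentence governs the primary denominator, and two programmers could read it differently. The ambiguity is itself the defect.
- **Redaction.** The text that would settle importance is blacked out: after the FAS definition in the protocol, after the primary test in both documents, and in both sample-size sections. If the null was set for patients with an evaluable lesion, type I error need not be inflated. That stands, and the error figures are conditional on it. It does not remove the conflict with the legible sentence in protocol 8.3.
- **Size.** Nothing visible supports E of 20% to 30%. Protocol 3.1 describes lesions as often diffuse and numerous, which points to a small E. The disagreement probability is highest near the decision boundary and falls below 0.1% at a true rate of 30%. Both points stand.
- **P-value convention.** The exclusion counts depend on it. Under the minimum-likelihood exact test, 16/100 gives p = 0.064 and becomes significant after 2 exclusions rather than 6. For p0 = 5% the nearest miss becomes 9/100 and needs 8 exclusions. The visible text does not name a convention, so the counts are examples only.

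None of this touches the contradiction or its direction.

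**Conclusion.** The concern holds and must be fixed before analysis. It is certain, on current and legible text, that the two documents give different denominators for the primary test. It is equally certain that the SAP's version can only leave the proportion unchanged or raise it relative to the FAS, which both documents name as the primary set.

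The size is not known. It is zero if every FAS patient has an evaluable lesion. At an assumed null of 10% the effect on type I error is negligible for E of 5% or less, and it becomes material at about 10% to 20%. Inflation arises only if the redacted null refers to the whole FAS; otherwise the problem is an undocumented change in the population to which the primary estimate applies. The case for correction rests on the contradiction and its direction, not on the conditional figures.

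**What to change.** In SAP 13.4, delete the words that add the evaluable-lesion condition, so that the sentence matches protocol 8.3. Add one sentence: *A FAS patient with no evaluable lesion counts as not meeting the primary endpoint.* The subset with an evaluable lesion may be reported as a labelled sensitivity analysis, with the number of patients it leaves out.

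The cost is one phrase deleted, one sentence added and one optional table. The reported proportion may be lower: 16.0% instead of 17.0% if 6 of 100 patients have no evaluable lesion, and by more if E is large (20% instead of 23.8% at E = 20%, f = 0). When making the edit, the sponsor should confirm that the redacted null and sample size refer to the whole FAS. If they were set for patients with an evaluable lesion, they need restating for the FAS; otherwise test and null would not match and power would fall.

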14 SAFETY EVALUATIONS

14.1 Overview of Safety Analysis Methods

Safety will be evaluated using the safety analysis set and will include treatment emergent adverse events (TEAEs), adverse device effects (ADEs), serious adverse events (SAEs), vital signs, physical examinations, clinical laboratory measurements, electrocardiograms, and concomitant medications. For all safety assessments, the baseline value will be the last non-missing value recorded for a particular safety parameter before exposure to study drug. In general, the analysis of safety will be descriptive. No data will be imputed except for partial dates if required to determine if an adverse event is treatment emergent or a medication concomitant with exposure to study drug.

14.1.1 Imputation of Partial Adverse Event Dates

If only a partial date is available and is required for a calculation, the following imputation algorithm will be applied for missing or partial dates related to Adverse Events and concomitant medications:

- [REDACTED]
 - [REDACTED]
 - [REDACTED]
 - [REDACTED]
- [REDACTED]
 - [REDACTED]

14.2 Extent of Exposure

Study drug will be administered as a single infusion. A summary of the number of patients exposed to study drug and any patients not receiving their full dose will be described. Start and stop times with respect to exposure to florescent light imaging will also be tabulated. More detailed study drug administration as well as camera start and stop times will be provided in line listings.

14.3 Adverse Events

Adverse events occurring prior to exposure to OTL38 administration will be provided in line listings. Treatment emergent adverse events (TEAEs) will be summarized via the Medical Dictionary for Regulatory Activities (MedDRA) system organ class and preferred term using patient incidence rates. Data will be tabulated by severity, physician assessment of relationship to study drug, serious TEAEs, and TEAEs leading to death or early study withdrawal. Further description of TEAEs may be defined by temporal onset to study drug infusion. Additional summaries of TEAEs identified as potential ADEs will also be provided.

Treatment-emergent AEs will be summarized for all patients in the safety analysis set. Summary tables will reflect the number and percent of patients experiencing at least 1 TEAE in each system organ class and preferred term. The overall number and percent of patients experiencing any treatment-emergent AE will also be provided. All percentages will use the number of patients in the safety analysis set as the denominator. An exception will be the presentation of ADEs which will use all patients undergoing fluorescent light imaging as the denominator. If a patient has more than one AE within a system organ class, the patient will be counted only once in that system organ class. If a patient has more than 1 AE that codes to the same preferred term, the patient will be counted only once for that preferred term. The tabular summary will be sorted by descending order of overall incidence.

Treatment-emergent AEs will also be summarized by the maximum relationship to study drug as determined by the Principal Investigator as well as the maximum severity of the event. Relationship to drug will be scored as Definite, Probable, Possible, or Not Related. Related AEs will be classified as those scored as Definite, Probable, and Possible. Severity will be rated as Mild, Moderate, or Severe. If a patient experiences more than 1 AE within system organ class or preferred term, that patient will be counted only once for that event under the maximum severity or most related category within the relevant category. In the event that the relationship to study drug or the severity of the event is missing, for tabulation purposes the maximum relationship or severity will be assumed.

Incidence of TEAEs will also be summarized by age group, race, and gender if there is sufficient numbers of patients within these subgroups. Otherwise only line listings will be provided.

All AEs will be presented in data listings for safety patients. If required, the line listings will distinguish between adverse events occurring prior to exposure to study drug and TEAEs. If a partial date was imputed, the line listings will include both the observed and imputed date. Imputations for missing relationships and severities of AEs will not be included in the line listings.

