5 TREATMENT ASSIGNMENT

The study design results in an open-label single-arm for the assessment of efficacy and safety. There is (are) no comparator group(s), and it is anticipated that all participating patients will receive OTL38. However, some patients receiving OTL38 will be randomized to undergo lesion assessment under normal light only and will not undergo fluorescent imaging. The goal of the randomization is not the assignment of patients to a comparator group, but to guard against the

possible “under-calling” of lesions during the normal light assessment by creating the possibility that any patient, following evaluation by normal light, may not continue to assessment by fluorescent imaging. To achieve this safeguard, a blinded randomization of patients to undergo fluorescent imaging, or not, will occur after normal light assessment, but prior to fluorescent imaging or surgery. The randomization will be generated from a single centralized randomization.

[REDACTED]

Patients receiving OTL38 and randomized to not to undergo fluorescent imaging will be evaluated for safety only.

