9 SUBJECT DISPOSITION AND PROTOCOL DEVIATIONS

9.1 Subject Disposition

Patient disposition will be summarized and include the following:

- The number of patients signing informed consent
- The number and percent of patients exposed to study drug
- The number and percent of patients randomized to each group
- The number and percent of patients who completed the study overall and by randomized group assignment

- The number and percent of patients who did not complete the study and the reason for early withdrawal overall and by randomized group assignment

Patients will be considered enrolled if they sign the informed consent (IC) and are exposed to study drug. Patients who signed the IC and receive study drug will serve as the denominator for the calculation of percentages. An exception will be the percentages calculated for early withdrawal reasons which will be based on the number of patients not completing the study. A data listing for all enrolled patients with regard to disposition will also be provided.

Patients who sign the IC but are not exposed to study drug will not be represented in any further analyses or line listings.

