9.2 Protocol Deviations

All protocol deviations will be recorded on the protocol deviation case report from (eCRF) and will be reported in line listings. Major protocol deviations will be identified prior to database freeze for the final analysis of endpoints other than [REDACTED] (see Section 15; Interim Analyses and Data Monitoring). Major protocol deviations will be analyzed by aggregate summary and line listings. For aggregate summaries, data will be presented overall and by randomized group assignment and for each analysis population. If the number of major protocol deviations is small, aggregate summaries will not be presented.

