10 SUBJECT DEMOGRAPHICS AND BASELINE CHARACTERISTICS

Descriptive statistics for patient demographics and baseline disease status will be provided. Demographics will be grouped by patients exposed to OTL38, patients randomized to no fluorescent light imaging, and patients randomized to undergo fluorescent light imaging, and overall randomized groups. If all patients exposed to OTL38 are subsequently randomized, the separate category for patients exposed to OTL38 may be omitted. Demographic variables will include, but are not limited to: age, sex, and race/ethnicity.

Baseline characteristics will include, but are not limited to: medical history, ovarian cancer history, ovarian cancer type, ovarian cancer stage, height, weight, and body mass index (BMI). Summaries will be tabulated for the mITT (FAS) group and the Safety Analysis Set. Individual demographic and baseline characteristics data will also be presented in line listings.

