14.4 Deaths, Serious Adverse Events and Adverse Events of Special Interest

Treatment-emergent serious AEs (SAEs), TEAEs leading to early study withdrawal, and TEAEs resulting in death will be summarized for all patients in the safety analysis set. Summary tables will reflect the number and percentage of patients experiencing at least 1 TEAE in each system organ class and preferred term within each AE subset (serious, leading to early study withdrawal, or death). In addition, the number of patients experiencing any TEAE in the respective subset will be reported. The tabular summary will be sorted by descending order of overall incidence.

Adverse events leading to early study withdrawal, AEs resulting in death, and SAEs will also be presented in data listings. Treatment-emergent AEs of special interest are those classified as infusion reactions which will be separately tabulated, or listed separately if numbers are not sufficient for meaningful summary statistics.

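### SAP 14.3 and 14.4 tabulate all-cause TEAEs and SAEs only for all dosed patients pooled; descriptive columns by randomised group would add the missing no-imaging rate (an improvement, not an error)

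*SAP*

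**What the plan says.** SAP 14.3: "Treatment-emergent AEs will be summarized for all patients in the safety analysis set". The denominator is the safety analysis set, which SAP 8.3 defines as every patient exposed to OTL38. SAP 14.4 treats serious events, events leading to early withdrawal and fatal events alike: "TEAEs resulting in death will be summarized for all patients in the safety analysis set". The only further TEAE splits named are age group, race and gender, and eligibility is limited to women.

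The one different denominator is for adverse device effects (ADEs): "An exception will be the presentation of ADEs which will use all patients undergoing fluorescent light imaging as the denominator".

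SAP 5 gives the reasoning: "The study design results in an open-label single-arm for the assessment of efficacy and safety". Randomisation is there to guard against under-calling of lesions under normal light and not to create a comparator. The same section adds: "Patients receiving OTL38 and randomized to not to undergo fluorescent imaging will be evaluated for safety only".

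Other parts of the SAP do report by randomised group:
- Disposition (9.1), including "the reason for early withdrawal overall and by randomized group assignment".
- Major deviations (9.2): "data will be presented overall and by randomized group assignment and for each analysis population", unless they are few.
- Demographics (10), with groups for "patients randomized to no fluorescent light imaging, and patients randomized to undergo fluorescent light imaging, and overall randomized groups".

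SAP 1 places the table shells in a separate document, which is not available here.

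**The concern.** Both randomised groups receive OTL38 and are assessed under normal light. Imaging, and any surgery it prompts, is what randomisation varies. The no-imaging patients are therefore a concurrent reference for the secondary objective on safety with the imaging system (SAP 2.2). They contribute to efficacy in no way, and in the described TEAE and SAE tables they appear only inside a total.

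The ADE table does not supply this reference. It has no no-imaging rate, and it holds only events that someone has judged to be a response to the device. The definition in Protocol 7.1 is broad and covers user error, but the judgement remains. The documents expect imaging to affect surgery: Protocol 3.4.2 lists removal of more lesions as a potential benefit, and SAP 13.3.4 counts imaging-driven changes of surgical plan. If a complication followed such added surgery, the investigator would decide whether to call it an ADE. The relationship scale in Protocol 7.4 concerns study drug. An all-cause rate by group depends on neither call.

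At stake is a missing comparison. The pooled figure itself would be only slightly off. For TEAEs and SAEs, a reader who wanted the two rates side by side would have to rebuild them from listings.

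**Working it through.** **Step 1. What is and is not shown by randomised group in the visible text**

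| Outcome | By randomised group? | Source |
|---|---|---|
| Withdrawal because of an AE or ADE | Yes, as a reason for withdrawal | SAP 9.1, with the reasons in Protocol 5.4 |
| Death recorded as the reason for withdrawal | Yes | SAP 9.1, with Protocol 5.4 |
| All TEAEs | No, pooled | SAP 14.3 |
| SAEs | No, pooled | SAP 14.4 |
| Organ class and preferred term detail of TEAEs leading to withdrawal or death | No, pooled | SAP 14.4 |
| ADEs | Imaged patients only | SAP 14.3 |

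The gap is rows three to five.

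**Step 2. Inputs for scale**

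The plan gives no safety rate or group size to reproduce. The only relevant figure is the minimum of 100 evaluable patients (Protocol Synopsis). The allocation ratio is redacted. Assumed here: 120 imaged patients; imaged to non-imaged ratios r of 1, 2, 3 and 9, so 120, 60, 40 and 13 non-imaged; all-cause risk 30% when imaged and 20% when not, or 30% in both.

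**Step 3. How far the pooled rate moves**

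Pooled rate = (0.30r + 0.20)/(r + 1).
- r = 1: 0.50/2 = 25.0%
- r = 2: 0.80/3 = 26.7%
- r = 3: 1.10/4 = 27.5%
- r = 9: 2.90/10 = 29.0%

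The shortfall from the imaged rate is 5.0, 3.3, 2.5 and 1.0 points. The more lopsided the allocation, the less the pooled figure is affected.

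**Step 4. Precision of a no-imaging column (Wilson 95% interval)**

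- 8/40 (r = 3): 10.5% to 34.8%
- 3/13 (r = 9): 8.2% to 50.3%
- For comparison, the imaged column, 36/120: 22.5% to 38.7%

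**Step 5. How often chance alone shows a gap**

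Let X1 ~ Bin(120, p1) and X0 ~ Bin(n0, p0) be independent. Sum the exact joint probabilities over |X1/120 − X0/n0| ≥ 0.10 for a chance gap, and over X1/120 ≤ X0/n0 for a hidden or reversed excess.

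| Ratio (n0) | Gap ≥ 10 points, 30% in both | Gap ≥ 10 points, 20% in both | Gap zero or reversed, true 30% v 20% |
|---|---|---|---|
| 1:1 (120) | 10.5% | 6.3% | 4.2% |
| 2:1 (60) | 18.6% | 12.9% | 7.6% |
| 3:1 (40) | 25.3% | 18.9% | 10.5% |
| 9:1 (13) | 46.8% | 39.0% | 19.2% |

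With 100 imaged patients and 30% in both groups, the chance-gap figures at 3:1 and 9:1 are 27.4% and 49.5%.

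**The case against.** The strongest reply is that this is a declared choice. SAP 5 calls the design single-arm for safety as well as efficacy, gives randomisation another purpose, and names no comparator. The objective is to assess safety with the imaging system, not to compare. That stands: a reader might infer that pooling contradicts the design or biases the safety results, and the documents support neither reading.

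A reader might also infer that nothing about safety is shown by randomised group. That goes too far. SAP 9.1 with Protocol 5.4 already gives withdrawals for AEs or ADEs, and deaths recorded as the reason for withdrawal, by group.

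The columns may also be too thin to be useful. At 9:1 the no-imaging group would hold about 13 patients, and chance gaps of 10 points would be common. This limits what the columns can say and rules out a test. It does not argue against showing the numbers with a clear label.

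The route from imaging to added surgery to an event not called an ADE is an inference. The documents state the first link as an expectation and do not state the rest. It explains why an all-cause rate is useful and is not evidence of harm.

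Finally, the shells are in a separate document and part of SAP 5 is redacted, so by-group safety columns may already be planned. The point is confined to the visible text.

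**Conclusion.** The point holds as a low-cost improvement. The SAP text describes no all-cause TEAE or SAE rate for the randomised no-imaging group, and no organ class or preferred term detail by group for events leading to withdrawal or death. It already reports disposition, deviations and demographics that way.

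The effect on the pooled percentage is small: 1.0 to 5.0 points across ratios from 9:1 to 1:1, under an assumed 30% against 20%. The value of the change is a concurrent reference that does not rest on a device-causality judgement. Because both groups are dosed, that reference speaks to imaging and any surgery it prompts, and says nothing about the drug. The risks, ratios and 120 imaged patients are assumptions, and none of the ratios shown is excluded by the documents. Across them the columns could neither confirm nor exclude a 10-point harm.

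**What to change.** - **SAP 14.3 and 14.4:** in the TEAE and SAE tables, and in the organ class and preferred term tables for events leading to withdrawal or death, add columns for randomised to imaging, randomised to no imaging, dosed but not randomised (if any) and total. Give each column its own denominator, label the display descriptive and run no test.
- **Randomised versus actual imaging:** footnote any patient randomised to imaging who was not imaged. Keep the ADE denominator as patients actually imaged.
- **Timing:** show events with onset before randomisation, such as during the infusion, separately where the recorded times allow. They cannot be due to imaging.
- **Shells:** if they already contain these columns, say so in the SAP text. Amending the single-arm sentence in SAP 5 is optional.

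The cost is extra columns in tables already planned, with no added patients or data fields. The downside is that a small no-imaging group will often show sizeable gaps by chance, so the descriptive label is essential.
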